### 3.5 Rationale of first dose of NPCs for the treatment of MS

The number of cells to be injected into patients via lumbar puncture has been chosen according to the data obtained in the preclinical trial we conducted in non human primates (Pluchino et al., 2009). The maximal dose of cells intracisternally injected in non human primates was  $5 \times 10^6$ /kg cells per animal. This is the very same maximal dose we will reach in humans, as we will start our dose escalating protocol from  $0.7 \times 10^6$ /kg cells per patient and, if no side effects will be recorded, we will proceed up to  $5.7 \times 10^6$ /kg cells per patients.

### 3.6 Risk benefit assessment

#### 3.6.1 Risk benefit definitions

*Risk* is defined as the probability of physical, psychological, social, or economic harm occurring as a result of participation in a research study. Both the probability and magnitude of possible harm in human research may vary from minimal to considerable.

*Minimal risk* exists where the probability and magnitude of harm or discomfort anticipated in the proposed research are not greater, in and of themselves, than those ordinarily encountered in daily life or during the performance of routine physical or psychological examinations or tests.

Risk above this standard is more than minimal (moderate, maximal) and that imposes limitations on the conduct of the research and increases the requirements for monitoring. It also requires more stringent approval processes when studying children or otherwise vulnerable populations. Increased risk should be accompanied by the probability of appropriately increased benefits.

*Benefit* applies to the potential of the research treatment to ameliorate a condition or treat a disease. This can apply to an individual participant or to a population. In research as in clinical medicine, results cannot be guaranteed but, as a consequence of prior work, a benefit may appear to be a reasonable expectation. Since this is research, an advantage for the treatment groups cannot be presupposed. Since the risks have not been fully evaluated, a statement of individual benefit should be made most cautiously if at all. The investigator should always distinguish between research and treatment and never lure the patient into participating in hopes of remission or cure.

[figure not shown]
### 3.6.2 Risk benefit ratio

The final goal of this study and future studies is to develop a curative treatment which can be offered to any patient affected by Progressive MS. The proposed clinical trial is designed to appropriately assess the safety of the ATIMP and applied procedures. The potential risks associated to the use of a novel technology and a reduced toxicity of immunosuppression regimen are well balanced by the potential benefit of a potentially curative therapy for patients to whom cannot be offered therapeutic options.

#### 3.6.2.1 Benefit

This approach might represent one of the first cell-based therapy promoting neuroprotection in diseases in which neurodegeneration is the final outcome of the tissue pathology. This is because, despite the initial perception that transplantation of NPCs could only serve to replace the lost cells, recent experimental studies from our own and other groups have shown that transplanted NPCs could also exert additional neuroprotective, as well as immunomodulatory, bystander effects capable of promoting tissue repair by preventing tissue damage, interfering with the pathogenic process, or rescuing endogenous neural cells (Kokaia et al., 2012). As a matter of fact, such results do support the concept that somatic stem cells might promote CNS repair via several and articulated strategies in inflammatory and degenerative disorders such as MS (see Figure 2).

**Figure 2 – Benefit assessment**

Transplanted NPCs adapt their fate and function(s) to specific environmental needs occurring as a result of different pathological conditions and therefore are capable of supporting neuroprotection not only by promoting cell replacement but also via the so-called bystander effect that is mainly aimed at rescuing endogenous neural cells. The bystander effect is made possible by the fact that NPCs sense the inflammatory environment (pathotropism) and, within such an environment, promote tissue homeostasis and repair by releasing, at the site of tissue damage (ectopic atypical perivascular niche), a milieu of constitutively expressed molecules capable of immunomodulation and trophic support. The net and final effect is neuroprotection because transplanted NPCs not only rescue damaged cells but also promote cellular and molecular plasticity. Thus, NPC transplantation might represent an ideal therapeutic strategy also in neurological disorders characterized by multifocal and diffuse inflammatory and degenerative processes caused by the maladaptive interactions among different cell types

### **3.6.2.2 Risk**

The risks the patients enrolled in the trial can be subjected to might be due to:

- (1) the procedure of cell injection per se (discussed in details other sections of this project);
- (2) allergic reactions to the medicinal product (discussed in details other sections of this project);
- (3) infections due the non sterility of the cell product: this risk has been very much minimized by the extensive in vitro examinations of the medicinal product we performed (see IMPD);
- (4) tumor formation: this risk has been minimized by the in vivo extensive assessment we have performed using supra maximal doses of cells infused in immunosuppressed mice (see preclinical in vivo toxicity data).

### **3.6.2.3 Ratio**

In conclusions, while the risk patients enrolled in the trial can be subjected to the risks that we usually take when we explore a new potential therapy, the benefits might overtly overcome the risks since the therapeutic approach we are proposing might represent one of the very first – if not the first - neuroprotective therapies for conditions in which neurodegeneration is due to neuroinflammation, i.e. progressive MS patients.

Moreover, if efficacious such therapy might also represent an approach to treat several other neurodegenerative/neuroinflammatory CNS disorders such as stroke and spinal cord injury.

## 4 Objectives

### 4.1 Primary Objective

The primary objective of the study is to evaluate the feasibility, safety and tolerability of intrathecally administered hNPCs, at an escalating dose ranging from  $0.7 \times 10^6 \pm 10\%$  cells to  $5.7 \times 10^6 \pm 10\%$  cells/kg of body weight, in patients affected by progressive MS.

## 5 Study design and Endpoints

### 5.1 Description of Study Design

This is a prospective, monocentric, national, therapeutic exploratory, phase I, not randomized, open label, not controlled, single dose escalation clinical trial.

### 5.2 Duration of study

Each subject will participate in the study for approximately 96 weeks. Participation will include a screening evaluation between -28 and -7 days before the ATIMP administration. A follow-up visits will be performed from 1 to 96 weeks.

### 5.3 Primary End-point

The following safety endpoints will be used to address the primary objectives:

#### a) SHORT TERM (0-24 hours)

- overall survival
- overall safety and tolerability measured by AE recording
- changes in neurological conditions not related to disease
- proportion of successful intrathecal administration procedure (feasibility)

Day 0 = hNPCs administration

#### b) MID TERM (day 1-day 14)

- overall survival
- overall safety and tolerability measured by AE recording
- changes in neurological conditions not related to disease

#### c) LONG TERM (day 15 - week 96)

- overall survival
- overall safety and tolerability measured by AE recording
- long term incidence of malignancies
- percentage of subjects with treatment-related mortality defined as death due to procedure and not to the course of disease
- evaluation of changes in quality of life measures
- changes in neurological conditions

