**AEs related to lumbar puncture and injection procedure:**

Lumbar puncture: is a minimally invasive, diagnostic or therapeutic procedure that involves the removal of a small amount of cerebrospinal fluid (CSF) - the fluid that surrounds the brain and spinal cord - followed by the injection of neural cells into the lumbar region of the spinal column. In this study, the quantity of collected CSF will be replaced by the same amount of cell culture medium.

The most frequent adverse events related to this procedure is the orthostatic headache and/or back pain. The frequency of these events is about 15-30%. Normally they resolve in few days and they can be treated with bed rest, anti-inflammatory drugs and hydration. The injection of any substance in the spinal canal could induce an inflammatory/irritative reaction with highly variable severity and duration of the AE. This kind of reaction is unpredictable.

Overall, rare adverse events (<1%) are related to the simple Lumbar Puncture Procedure and consist in: risk of infection; risk of bleeding (epidural or subdural hematoma); risk of cranial nerve palsy and cauda equina syndrome; hypotension, bradycardia with or without syncope.

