**5.5.2.1 Documentation of (serious) AE**

Between screening and last follow-up visit the patient will be asked and examined by the investigator for the occurrence of AEs. All AEs will be documented using CTCAE terms (see Appendix), including

- Severity (listed under)
- Onset date
- Stop date
- Causality assessment with study drug
- Action taken
- Outcome

The severity of AEs is defined as (see also CTCAE):

- Grade 1 mild
- Grade 2 moderate
- Grade 3 severe
- Grade 4 life-threatening
- Grade 5 death

All clearly related signs, symptoms and abnormal diagnostic procedures should be grouped together and recorded as a single term in the CRF.

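### Treatment-related mortality, a primary endpoint, is listed only from day 15, so on a literal reading a death from the day-0 injection procedure on days 0-14 is left out of the percentage

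*Combined protocol and SAP*

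**What the plan says.** Section 5.3 introduces its three lists with "The following safety endpoints will be used to address the primary objectives", so everything in them is primary. The lists are headed "SHORT TERM (0-24 hours"), "MID TERM (day 1-day 14") and "LONG TERM (day 15 - week 96"). The third contains "percentage of subjects with treatment-related mortality defined as death due to procedure and not to the course of disease"; the first two do not. The synopsis has the same layout. No section says that the percentage accumulates from day 0, and none states its denominator.

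Day 0 is the day the cells are given (section 5.3 a). Section 7.1 describes one lumbar puncture with injection, followed by at least 24 hours of monitoring. If the puncture is traumatic, the injection is not done and a second attempt follows after 15 ± 3 days. A further lumbar puncture, for CSF sampling, is planned at week 12 (section 8.3.5).

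For every adverse event, section 5.5.2.1 asks for "Causality assessment with study drug" and grades death as 5. Section 11 plans descriptive statistics only and leaves the detail to an analysis plan still to be written.

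**The concern.** The endpoint is meant to isolate deaths caused by the procedure, yet its listed window opens two weeks after the injection. It leaves out the injection itself, the monitored hospital stay, the three-hour acute-toxicity period of section 5.5.1 and the whole mid-term period.

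At stake is a headline primary result. A trial in which a patient died from the injection in the first two weeks could report 0% treatment-related mortality while following its protocol exactly. Two analysts with the same data could also report different values, one using the listed window and one assuming the percentage was meant to be cumulative.

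**Working it through.** **1. Is the placement a window, or just a place to put the bullet?** The lists in section 5.3, side by side:

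| Endpoint | 0-24 h | Day 1-14 | Day 15-week 96 |
|---|---|---|---|
| Overall survival | yes | yes | yes |
| Safety and tolerability by AE recording | yes | yes | yes |
| Success of the administration procedure | yes | no | no |
| Malignancy | no | no | yes |
| Quality of life | no | no | yes |
| Treatment-related mortality | no | no | yes |

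Endpoints meant for all periods are repeated in each list. Those tied to one period appear once, such as "proportion of successful intrathecal administration procedure (feasibility"). By that convention, treatment-related mortality belongs to day 15 onward only.

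**2. Does another endpoint supply the missing figure?**
- Overall survival counts the death but gives no cause.
- AE recording counts it as grade 5, but the causality field (5.5.2.1), the attribution scale (5.5.3.1) and the investigator's opinion (5.5.7) all concern the product, not the procedure.
- The DLT definition (7.10) does cover the procedure, but it serves an escalation rule and yields no mortality percentage.

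So no listed endpoint gives a procedure-attributed death percentage for days 0-14.

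**3. Inputs.** Four cohorts of at most 6 give 4 × 6 = 24, which reproduces the stated maximum (synopsis and 8.1). Four cohorts of at least 3 (7.10) give 4 × 3 = 12. Week 96 is day 96 × 7 = 672, so days 0-14 are 15 of 673 days (2.2%).

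**4. Illustration.** Assume one procedure death on days 0-14 and none later. Intervals are two-sided exact (Clopper-Pearson) 95% throughout. For 0/n the upper limit is 1 − 0.025^(1/n). For 1/n the lower limit is 1 − 0.975^(1/n), and the upper limit p solves (1−p)^n + n·p·(1−p)^(n−1) = 0.025.

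| Patients | Literal window | Counted from day 0 |
|---|---|---|
| 24 | 0/24 = 0% (0-14.2%) | 1/24 = 4.2% (0.1-21.1%) |
| 12 | 0/12 = 0% (0-26.5%) | 1/12 = 8.3% (0.2-38.5%) |
| 3 (one cohort) | 0/3 = 0% (0-70.8%) | 1/3 = 33.3% (0.8-90.6%) |

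If only patients alive at day 15 are counted, the literal results are 0/23 (0-14.8%) and 0/11 (0-28.5%). The text does not say which denominator applies.

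**5. Cohort expansion.** The 12-patient row assumes that no cohort expands. If the death counts as a DLT, its cohort goes to 6 (7.10), and four completed cohorts hold at least 3 + 3 + 3 + 6 = 15 patients. The contrast is then 0/15 against 1/15 = 6.7%. Whether a fatal event is a DLT is itself unclear: the definition in 7.10 speaks of grade 3, while the safety board trigger in the same section is grade 3 or above. Those two sentences must be reconciled.

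**The case against.** The strongest answer is that an early procedure death cannot disappear. Survival and AE recording are primary in both early windows. The death is a grade 5 event with a causality entry, and it is reported as a serious event within 24 hours (Table 2). The safety board reviews the safety data before each cohort shift (7.10), and autopsy is encouraged (6.3.1). Escalation is governed by DLTs, not by this percentage. All of this stands. A reader might infer that the death would go unnoticed, or that its cause would go entirely unexamined; the documents do not support either inference.

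Second, a percentage given at the last horizon can be read as cumulative, and that is probably what the authors intended. But the heading names a start day and nothing overrides it. Because other endpoints are repeated by window, the cumulative reading is a guess.

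Third, a reader might infer that the protocol shows procedure deaths to be most likely on days 0-14. It does not. Section 5.5.2 lists rare complications of lumbar puncture, among them "risk of bleeding (epidural or subdural hematoma"), without timing or risk of death. Its only duration, a few days, concerns headache and back pain. Early clustering is plausible from that list and from the three-hour toxicity window in 5.5.1, but it remains an assumption.

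Fourth, the later window is not empty of procedures, since the week-12 lumbar puncture falls in it. That gives a reason to include the period after day 15, but none to leave out the period before it.

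**Conclusion.** The point holds as a flaw in the definition of a primary endpoint. On the text as written, a procedure death on days 0-14 is excluded from treatment-related mortality, and no other listed endpoint gives a procedure-attributed percentage for those days. One such death moves the result between 0% and 4.2% at 24 patients, 6.7% at 15, or 8.3% at 12. The intervals overlap heavily, as they must at these sizes, so what is at issue is whether the death is counted, not precision.

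The conclusion rests on reading the window headings literally. The figures rest on the assumed single early death with none later. The window error does not depend on when procedure deaths tend to occur.

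This should be fixed, but it does not threaten the conduct of the trial: the death remains visible in other primary endpoints and in safety reporting, and no escalation decision uses this percentage.

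**What to change.** In section 5.3 and the synopsis, take treatment-related mortality out of the long-term list and define it once, as cumulative from the start of the first study lumbar puncture to week 96. The denominator is all patients who undergo a study lumbar puncture, with the same percentage also shown for those who received hNPCs. Starting the clock at the first puncture matters because a traumatic puncture stops the injection. A death before the second attempt would precede day 0, and that patient would be missing from a denominator of treated patients.

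Show the result by window as well, assigning each death to one window only, since the first 24 hours can run into day 1. For each death, record relation to the procedure alongside relation to the study drug, name who makes that judgement, and say whether the week-12 puncture counts as the procedure. Carry the same wording into the analysis plan.

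The cost is a few lines of text and one extra item on the form for deaths. No new visits, tests or patients are needed, because deaths are already recorded from the outset.

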### 5.4 Research endpoints

The research endpoints are evaluated to obtain preliminary data on the effect of hNPCs in patients affected by progressive MS.

### 5.5 Safety criteria

#### 5.5.1 Safety profile (hNPC cells)

The safety profile of hNPCs cells are unknown. Other heterogenic clinical studies on Parkinson disease, ataxia-teleangectasia, Huntington disease, spinal cord injury and inherited cerebellar atrophy were conducted and two cases of late onset graft-derived tumours were observed. To

date hNPCs cells have never been used in Multiple Sclerosis. However, two phase I trials and one phase II trial have been performed in adult patients affected by Amyotrophic Lateral Sclerosis and other two phase I trials have been performed in children affected by neuronal ceroid lipofuscinosis and Pelizaeus-Merzbacher disease. The total number of patients exposed to hNPCs are 42. In all these studies a surgical injection of stem cell directly in the brain or the spinal cord was performed. Overall no side effects or adverse events related to hNPCs were reported. Also anatomo-pathological studies conducted in subjects who died during the follow-up of the previous studies for the underlying disease confirmed the feasibility and the therapeutic potential of this treatment.

Preclinical studies in non-human primates with hNPCs did not shown any safety issue.

The safety profile will be monitored from the baseline visit to the last follow-up visit.

The SHORT TERM safety profile will be evaluated trough:

- **Vital signs:** During the injection of hNPCs vital signs including oxygen saturation will be monitored before and then after 15 minutes, 60' and 3 hours after the end of injection. Vital signs will be then monitored before discharge.

Particularly, during the treatment visit acute injection toxicity and allergic reactions will be monitored, and it will be defined as any of the following events within three hours post injection:

- Systolic blood pressure (mmHg) <90 or >180, or >33% decrease or increase from baseline
- Diastolic blood pressure (mmHg) <50 or >100, or >33% decrease or increase from baseline
- Heart rate: <60 or >33% decrease; >110 or >33% increase
- Oxygen saturation: hypoxia (grade  $\geq 2$  according to CTCAE)
- Body temperature ( $^{\circ}\text{C}$ ) >37.5 $^{\circ}\text{C}$  or >1 $^{\circ}\text{C}$  increase
- Any other toxic side effect (according to CTCAE)

- Physical examination will be performed before the hNPCs injection and before the discharge of the patient.

- Neurological examination will be performed before the hNPCs injection and before the discharge of the patient.

All new or worsening neurological signs and symptoms will be monitored, evaluated and recorded. In the presence of newly identified or worsening of neurological sign or symptom the investigator should assess whether the patient is experience a relapse of MS or another neurological (non-MS related) disorder.

- Cerebrospinal fluid examination (CSF): a CSF examination will be performed in concomitance with hNPCs administration.

- Routine Clinical Laboratory tests will be performed before the hNPCs injection and before the discharge of the patient (see appendix for detailed tests).

The following procedures might be performed, at investigator discretion, in the presence of a new or worsening neurological or systemic condition:

- Haematology and biochemistry examination complete of Erythrocyte Sedimentation Rate/Velocity (ESV) and CRP
- Chest X ray
- Brain and spinal cord Magnetic Resonance Imaging (MRI) with gadolinium
- Lumbar puncture

- Electrocardiography (EKG)

MID TERM (DAY 1 – DAY 14) safety profile will be evaluated trough:

- Vital signs including oxygen saturation will be monitored during visit at week 1 and week 2.
- Physical examination will be performed during visit at week 1 and week 2.
- Neurological examination: a neurological examination will be performed during visit at week 1 and week 2.

All new or worsening neurological signs and symptoms will be monitored, evaluated and recorded. In the presence of newly identified or worsening of neurological sign or symptom the investigator should assess whether the patient is experience a relapse of MS or another neurological (non-MS related) disorder.

- Haematological evaluation: will be performed during visit at week 1 and week 2.
- Routine Clinical Laboratory tests will be performed during visit at week 1 and week 2 (see appendix for detailed tests).

The following procedure might be performed, at investigator discretion, in the presence of a new or worsening neurological or systemic condition:

- Haematology and biochemistry examination complete of ESV e CRP
- Chest X ray
- Brain and spinal cord MRI with gadolinium
- Lumbar puncture
- EKG

The LONG TERM safety profile will be evaluated trough:

At every scheduled visit the following procedures will be performed:

- Vital signs
- Physical examination
- Neurological examination
- Clinical Laboratory tests
- Haematological evaluations
- Instrumental follow-up:
  - Week 48 and week 96 electrocardiogram, chest Xray;
  - Week 96 abdominal ultrasound.

- Administration of MsQuol54 will be performed at 24, 48 and 96 weeks.
- Brain and spinal cord MRI with gadolinium: will be performed at 12, 24, 48 and 96 weeks.
- Cerebrospinal fluid examination (CSF): a CSF examination will be performed 12 weeks  $\pm$  2 weeks after hNPCs administration.

All new or worsening neurological signs and symptoms will be monitored, evaluated and recorded.

In the presence of newly identified or worsening of neurological sign or symptom the investigator should assess whether the patient is experience a relapse of MS, any neurological disorder related to the recent injection procedure or any other neurological (non-MS related) disorder.

The following procedure might be performed, at investigator discretion, in the presence of a new or worsening neurological or systemic condition:

- Haematology and biochemistry examination complete of ESV e CRP
- Chest X ray
- Brain and spinal cord MRI with gadolinium
- Lumbar puncture
- EKG

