**MS RELAPSE VISIT**

The assessment, management and reporting of MS relapse is made by the Primary Treating Physician.

MS relapse definition: appearance of a new neurological abnormality or worsening of previously stable or improving pre-existing neurological abnormality, separated by at least 30 days from onset of a preceding clinical demyelinating event (McDonald et al. 2001). The abnormality must have been present for at least 24 hours and occurred in the absence of fever (< 37.5°C) or known infection. MS relapse is defined as: any perceived change in symptoms or signs that persist for ≥ 48 hours in the absence of flu or fever and that is accompanied by objective changes on EDSS functional subscores (FSS) that leads to either a 1.0 point change in EDSS (for baseline EDSS 3 - 5.0) or a 0.5 change (for baseline EDSS ≥ 5.5) together with FSS changes of 2 points in any one FSS or 1 point in any 2 FS. Only relapses meeting the protocol definition will be considered as measure of efficacy.

Diagnosing MS relapses during the study: Patients will be instructed to immediately contact the Primary Treating Physician if he/she develops new or re-occurring or worsening neurological symptoms. If a patient reports new neurological symptoms or worsening of previous symptoms, an unscheduled visit is to be planned as soon as possible, ideally within 7 days. During this visit, the treating physician will first assess whether the new/worsening neurological abnormality is consistent with the definition of MS relapse above.

If so, the standard neurological examination (for the EDSS score) should be performed by the Independent EDSS Rater. If there is any doubt in the opinion of the treating physician, the default must always be to refer the case to the Independent EDSS Rater to perform an EDSS rating.

Confirmation of MS relapse: the definition of a confirmed MS relapse is one accompanied by a clinically relevant change in the EDSS performed by the Independent EDSS Rater, i.e. an increase of at least 0.5 points on the EDSS score, or an increase of 1 point on two FSs or 2 points on one FS, excluding changes involving bowel/bladder or cerebral FS compared to the previous available rating (the last EDSS rating that did not occur during a relapse).

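### Up to day 14 the primary neurological endpoint leaves out disease-related changes and the assessment names neither the procedure nor the cells, so a treatment-provoked, MS-like worsening can drop out of that component

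*Combined protocol and SAP*

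**What the plan says.** **Endpoint.** Section 5.3 a) defines the short-term neurological endpoint as "changes in neurological conditions not related to disease". Section 5.3 b) repeats this for days 1-14. Section 5.3 c), from day 15 to week 96, has only "changes in neurological conditions". The synopsis (1.1) has the same split. No reason is given for the change at day 15.

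**Assessment.** For new or worsening neurological signs in the short and mid term, section 5.5.1 tells the investigator to "assess whether the patient is experience a relapse of MS or another neurological (non-MS related) disorder". In the long term the options become "a relapse of MS, any neurological disorder related to the recent injection procedure or any other neurological (non-MS related) disorder". No window names the cells or MS progression.

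**Recording.** Section 5.5.1 also states: "All new or worsening neurological signs and symptoms will be monitored, evaluated and recorded". In all three windows a second primary endpoint applies, "overall safety and tolerability measured by AE recording", with no limit by cause.

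**Relapses.** The MS relapse visit text in 8.3.5 says: "Only relapses meeting the protocol definition will be considered as measure of efficacy".

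**The concern.** The trial is open label and has no control arm, so the attributed cause decides whether an early neurological event enters this component of the primary endpoint. The days after injection are when an effect of the cells or the procedure is most plausible. They are also the days when disease-related changes are left out and the procedure is not offered as an explanation. The procedure option appears from day 15, when the injection is no longer recent.

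The protocol itself foresees such an event. In 5.5.2, on lumbar puncture and injection, it warns that any substance put into the spinal canal may cause an inflammatory or irritative reaction of unpredictable severity. Section 5.5.1 says the safety profile of the cells is unknown and that they have not been used in MS. If a reaction of this kind looks like MS, relapse is its natural label. The early neurological count would then understate harm, and it could not be read alongside the later count.

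**Working it through.** **Step 1. The windows side by side.**

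| Window | Changes counted (5.3) | Options offered (5.5.1) | Event labelled relapse |
|---|---|---|---|
| 0-24 h | only those unrelated to disease | relapse; other non-MS disorder | not counted |
| Day 1-14 | only those unrelated to disease | relapse; other non-MS disorder | not counted |
| Day 15-week 96 | all | relapse; injection procedure; other non-MS disorder | counted |

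The limit by cause applies in two of three windows. There are two options up to day 14 and three afterwards. None names the cells and none names progression.

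**Step 2. Can a treatment-provoked event carry the relapse label?** The definition in 8.3.5 asks for a new or worse neurological abnormality of sufficient duration and rules out fever and known infection. It does not rule out a reaction to the cells or the procedure, so an MS-like reaction can meet it. With that label an event on day 5 is left out of the component. The same event with the same label on day 20 is counted. A day 5 event labelled as a non-MS disorder is also counted. In the early windows, then, inclusion turns on the label alone.

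**Step 3. Where else is the event captured?**
- AE recording is a primary endpoint in every window (5.3).
- Section 5.5.2.1 requires a causality assessment against the study drug for each AE, and 5.5.3.1 gives a five-level scale.
- Section 5.5.7 requires all AEs in the CRF, whatever their seriousness or cause.
- Section 7.10 makes a grade 3 event a DLT if the cells or the procedure are a possible cause. Relapse is not among its exclusions.

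Two passages conflict with 5.5.7. Table 2 in 5.5.2.2 documents non-serious events in the patient's chart only. The end of the infective-complications text in 5.5.2 reports events from concomitant medication and procedures only above grade 3. If that text covers the injection procedure, a grade 3 procedure event would be a DLT under 7.10 and yet fall below the reporting threshold.

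**Step 4. How much background does the early exclusion remove?**
- Patients: four cohorts of three give 4 x 3 = 12 if all cohorts open without expansion. Four of six give 4 x 6 = 24, which matches the stated maximum.
- Relapse rate r: the documents give none. Assumed 0.1 to 0.5 per patient-year.
- Expected coincidental relapses in 14 days: E = n x r x 14/365.25.
- Chance of at least one (Poisson): 1 - exp(-E).

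| n | r | E | Chance of at least one |
|---|---|---|---|
| 12 | 0.1 | 0.046 | 4% |
| 12 | 0.5 | 0.230 | 21% |
| 24 | 0.1 | 0.092 | 9% |
| 24 | 0.5 | 0.460 | 37% |

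Across the whole trial, fewer than half a coincidental relapse is expected in the early windows.

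**The case against.** The strongest reply is that nothing is lost from safety. A reader might infer that a relapse-labelled event leaves the safety assessment altogether. The documents do not support that: the event leaves one component, for days 0-14 only, and Step 3 shows where it should still appear. Section 5.5.1 asks for a clinical differential diagnosis. Causality is rated elsewhere, and no text lets the relapse label settle that rating. A reaction that does not resemble MS fits the non-MS option and stays in the component. The safety board also reviews all data before each cohort change. All of this stands, and it limits the point to a risk in one component. The AE route is nevertheless weakened by the conflicting recording rules.

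A reader might also infer from 8.3.5 that relapses are moved from safety to efficacy. That sentence only restricts which relapses count for efficacy; AEs and relapses are both recorded at every scheduled visit. An independent EDSS rater also confirms relapses, so the label is not the treating physician's alone. However, that confirmation concerns the size of the EDSS or functional-system change, not its cause.

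The absence of a progression option matters little early on, since 5.6 requires confirmation at least 12 weeks later. A relapse must also last 24 hours (48 in the second definition), so it can hardly be established within 0-24 hours. Finally, section 11 plans descriptive statistics only, with no comparison or sum across windows. That lowers the stakes but does not explain why one endpoint has two definitions.

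**Conclusion.** The point holds in limited form. The definition changes at day 15 without explanation, and the early assessment lacks the procedure and the cells. Together these allow a treatment-provoked, MS-like worsening in days 0-14 to drop out of the neurological-change component. It should remain an AE with its own causality rating and can be a DLT, subject to reconciling 5.5.2, Table 2 and 5.5.7.

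The exclusion gains little: 0.05-0.23 expected coincidental relapses for 12 patients and 0.09-0.46 for 24, on an assumed rate of 0.1-0.5 per patient-year. A reader might infer that most early relapses would then be caused by treatment. That does not follow. The share depends on the unknown rate of provoked events, and at the upper end of the assumed range the chance of at least one coincidental relapse among 24 patients is 37%. The textual finding does not depend on the assumed rate.

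**What to change.** - In 5.3 a), b) and c) and in the synopsis, use one definition: all new or worsening neurological signs against the pre-injection (day -1) examination, whatever the attributed cause.
- In 5.5.1, use one attribution list in all three windows: MS relapse, MS progression, injection procedure, hNPCs, immunosuppression, other. Report attribution as a breakdown of the all-cause count.
- Tabulate relapses in days 0-14 as safety events as well as MS events.
- Reconcile 5.5.2, Table 2 and 5.5.7 on which AEs are reported and reach the CRF.

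The cost is protocol wording and one CRF field, since 5.5.1 already requires all such signs to be recorded. The downside is that the reported early event rate may be higher and will include some coincidental MS events. No dose or clinical rule changes.
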